## 15.6 Participant Eligibility, Informed Consent, and Calendly Messages

### Message prompt for Eligible Participants :

Thank you for your interest in the Digital Smoking Cessation Study! You may be eligible to enroll in the study. To help you decide if you'd like to take part in this smoking cessation study, this form will tell you about the trial and what it will involve. Before you make your decision, it is important for you to understand the study and get detailed information about the study. Please take as much time as you need to read through this information. If you have any questions, please discuss them with the investigator or research coordinator prior to consent.

**\*\*PLEASE BE AWARE** that you will not be able to return to the Participant Information & Informed Consent form after closing the document from your internet browser. Please **DO NOT** exit from the informed consent form link until your questions about the study or consent (if you have any) have been discussed with the research coordinator.

Here is the **[LINK]** for the Digital Smoking Cessation Study: Participant Information & Informed Consent

If you have any questions, please contact the research coordinator at [[contact]](mailto:[contact]) or [contact].

**Message prompt for Ineligible Participants :**

Thank you for your interest in the Digital Smoking Cessation Study! Unfortunately, **you are not eligible** [to participate]. For help with quitting smoking, please go to [www.smokefree.gov](http://www.smokefree.gov) or call [name].

**Baseline Survey + Participant ICF Reminder Message :**

Thanks again for your time and willingness to participate in our study! Please check your email as we just sent you the link to complete the baseline survey + your signed copy of the consent. You only have 1 week to complete the baseline survey before the link expires.

If you have trouble viewing the baseline survey link from your personal email or have any questions, please contact the research coordinator at [contact] or email [[contact]](mailto:[contact])

**Baseline Survey + Participant ICF Reminder Message :**

Thank you for your interest in the Digital Smoking Cessation Study! Please check your email for a copy of your signed informed consent. If you are unable to review your signed informed consent or have any additional questions - please contact the research coordinator at [contact] or email [[contact]](mailto:[contact])

**Calendly Schedule Message :**

Thank you for submitting the Baseline Survey/Outcome Survey!

Please click the Calendly link below to schedule the Randomization Call/Live Video Monitoring Call with the research coordinator. If you have any questions regarding scheduling

the randomization phone call/live video call, please contact the research coordinator at [contact] or email [[contact]](mailto:[contact])

Tap this **[LINK]** to schedule the Randomization Call/Live Video Monitoring Call via Calendly

## 15.7 **Baseline Survey + Participant ICF Email**

Baseline survey link + Participant ICF copy email

**Subject Line: Digital Smoking Cessation Study- Next steps to enroll**

Thank you for your interest in the Digital Smoking Cessation Study! You may be eligible to enroll. The next steps in the enrollment process are in the Baseline Survey and Randomization phone call with the research coordinator. You will have 7 days from now to submit the Baseline survey + schedule the randomization call to complete your eligibility for the study.

Tap this **[LINK]** to get started on the baseline survey!

Attached is your signed copy of the informed consent. If you have any questions, please contact me at [contact] or email [[contact]](mailto:[contact])

Thank you!

Participant ICF copy email

**Subject line: Digital Smoking Cessation Study- Participant signed informed consent**

Thank you for your interest in the Digital Smoking Cessation Study. Attached is your signed copy of the informed consent.

We wish you all the best,

My Digital Study Team

## 15.8 **Randomization Email**

Hi [Name],

It was so nice speaking with you today. Thanks again for your time and willingness to participate in our study. This code will allow installation on one iOS or Android device only and may not be shared with other individuals.

**1.) Here is the link for the assigned treatment application: [LINK]**

**2.) The link to download the iCO Smokerlyzer application can be found here: [LINK]**

Please don't hesitate to contact me should you have any questions after our phone call at [contact] or email [[contact]](mailto:[contact])

Thank you!

## 15.9

### Welcome Email & SMS

Congratulations! You are now enrolled in the Digital Smoking Cessation Study. The purpose of this research study is to compare the effectiveness of two commercially-available smoking cessation applications ("apps") designed for your smartphone. Each app is intended to help users smoke less and eventually quit. We thank you for choosing to be a part of this study and helping to support further development of this digital treatment option for smoking cessation.

You will be in the study for at least 8 weeks. During the study, you will be required to complete an 8-Week Outcome Survey and submit an exhaled carbon monoxide assessment via your iCO Smokerlyzer device. The Smokerlyzer device will be a part of the welcome package that will be mailed to you after the randomization phone call. If you do not receive the My Digital Study Welcome Package within 2 weeks, please contact the research coordinator.

All participants in the study will be eligible to receive \$100, paid in Amazon gift cards (gift cards will be paid to the participant in \$50.00 increments), for completion of the 8-week Outcome Survey, and the 8-week Carbon Monoxide Assessment. A subset of participants will be invited to conduct the 8-week carbon monoxide assessment via live video monitoring at the end of the outcome survey. Participants will also receive an additional \$50 Amazon gift card for submitting the exhaled CO assessment via live video monitoring.

Be sure to contact the research coordinator with any additional questions you may have at [contact] or email [[contact]](mailto:[contact])

Tap this [LINK] for the iCO Smokerlyzer device video instructions ☺

Sincerely,

The My Digital Study Team

**Welcome SMS:** Welcome!! You are now enrolled in the Digital Smoking Cessation Study. If you have any questions, please contact the research coordinator at

[[contact]](mailto:[contact]) or [contact]. Tap this **[LINK]** for the iCO Smokerlyzer device video instructions ☺

## **15.10 Participant SMS & Email Messages: Baseline, Week 4, Day 53, Day 56, F/U**

### **a. Baseline Survey SMS**

Thank you for your interest in the Digital Smoking Cessation Study! You may be eligible to enroll by completing the next steps in the enrollment process: baseline survey and randomization phone call.

You will have 7 days from now to submit the Baseline survey to complete your eligibility for the study. Tap this **[LINK]** to get started on the baseline survey!

### **b. Smokerlyzer Check Week 4 (Day 28) Email and SMS**

#### **Subject Line: Digital Smoking Cessation Study- Week 4 (Day 28) Smokerlyzer Check**

Congratulations [name]! You're halfway there! By submitting the Smokerlyzer CO assessment, you are helping us confirm that the device works! Please submit your Smokerlyzer assessment now. If you have any questions or have not received your Smokerlyzer please contact [name] at [contact] or email [[contact]](mailto:[contact]). Keep up the good work!

Tap this **[LINK]** for the Smokerlyzer video instructions ☺

Sincerely,

The My Digital Study Team

**Week 4 SMS:** Congratulations [name]! You're halfway there! By submitting the Smokerlyzer CO assessment, you are helping us confirm that the device works! Please submit your Smokerlyzer assessment now. Tap this **[LINK]** for the Smokerlyzer video instructions ☺

### **3. Day 53 EOS Assessment Email**

#### **Subject Line: Digital Smoking Cessation Study- 8-week Outcome Survey**

You're almost there! Whether you were able to quit or not, make sure to complete the outcome survey and Smokerlyzer CO assessment. Don't forget that everyone who finishes the study can earn up to \$150 in Amazon gift cards regardless of current quit status.

Tap this **[LINK]** to get started on the outcome survey!

Tap this **[LINK]** for the Smokerlyzer video instructions ☺

Sincerely,

The My Digital Study Team

#### 4. EOS Thank you SMS

- a. Congrats, [name]! You've completed the smoking cessation study at My Digital Study! You've worked hard on this journey. Feel free to continue using [CKT or QG] or even after the study's official completion. Don't give up on your goal to quit, Great work!!
- b. \*\*\*Our team would like to thank you for completing the smoking cessation study. We wish you the best of luck and hope that you enjoyed your experience!!

### 15.11 User SMS & Email Reminders: Baseline, Week 4, CO prompt, Day 56, F/U

#### Baseline Survey Reminder

- a. Hi [name], this is [name] from My Digital Study... Don't forget to fill out the baseline survey by [deadline]! Remember, you are eligible for up to \$150 for completing the study! Pretty cool, right? Tap this link to get started:
- b. Hi [name], this is [name] from My Digital Study for your 2nd follow-up reminder to complete the baseline survey by [deadline date]!.. Did you know you have only 7 days to complete the baseline survey before the link expires?!? Start the baseline survey before it expires! Tap this link to get started:

#### Smokerlyzer Check Week 4 (Day 28) Reminder

- a. Don't forget [name]! You're Smokerlyzer Test is waiting for you! Please submit your Smokerlyzer CO assessment now to receive up to \$150 in Amazon gift cards at the end of the study. Keep up the good work!
- b. Hi [Name]! This is your final reminder to complete your Smokerlyzer Assessment. We appreciate your participation with submitting your results, regardless of the outcome! If you have not received your Smokerlyzer or are experiencing technical difficulties, please contact [name] at [contact] or [[contact]](mailto:[contact])

#### Submitted Outcome Survey prompt reminder for the EOS CO Assessment

Thank you for submitting the 8-week Outcome Survey!

Please remember to submit your Smokerlyzer CO assessment if you have not done so already. If you have any questions, please contact the research coordinator at [contact] or email [[contact]](mailto:[contact])

Thank you!

### Day 53/56 EOS Assessment Reminder

- a. You're almost there! Whether you were able to quit or not, make sure to complete outcome survey and CO assessment. Start the outcome survey before it expires! Don't forget that everyone who finishes the study is guaranteed \$150 in Amazon gift cards!
- b. Whether you were able to quit or not, everyone in our study is now eligible to make up to \$150 in amazon gift cards for completing the study. Pretty amazing, right?? All you need to do is finish the outcome survey plus the CO assessment and those Amazon gift cards are all yours!! Tap this link to get started:
- c. \*\*\*Whether you were able to quit or not, everyone in our study is now eligible to make up to \$150 in Amazon gift cards! All you need to do is finish the [ outcome survey and /or the CO assessment] and those Amazon gift cards are all yours.
- d. Hi- this is [name] with my Digital Study. Don't forget to fill out the (outcome survey + Smokerlyzer) so you can receive up to \$150 in amazon gift cards! Did you know you have only 7 days to complete the outcome survey before the link expires?!? Here's the link to start the outcome survey before it expires on [date]!

### Day 1 & Day 2 Follow-up SMS & Email

- a. Hi Click or QuitGuide User! Don't forget to submit your [Baseline survey, Week 4- CO submission, EOS Outcome survey, EOS CO Assessment]. Thank you for participating in our study! Remember all of the reasons you decided to start your quit journey and stay strong! Here's the link again [no link for week 4 adherence check]
- b. Hi [name]! Please don't forget to complete the [Baseline survey, Week 4 CO assessment submission, EOS Outcome Survey, EOS CO Assessment]. This is a great way to track your progress and important for our study. Thanks for all of your hard work! Here's the link:

## **15.12 Voicemail Script**

Baseline Survey Voicemail Script: Hi [name], this is [name] from My Digital Study! I was just calling to follow-up your submitted baseline survey. Remember you only have 7 days to complete the baseline survey before the link expires. Start the baseline survey by [date] to be included in the study- participants can earn up to \$150 at Week 8- End of Study Completion.

Smokerlyzer Assessment Check (Day 28) Voicemail Script: Hi [name], this is [name] from My Digital Study! I was just calling to remind you to submit your Day 28 Smokerlyzer assessment. By submitting the Smokerlyzer CO assessment, you are helping us confirm that the device works! We appreciate your participation with submitting your results, regardless of

the outcome! If you have not received your Smokerlyzer or are experiencing technical difficulties, please contact me [name] at [contact] or email [[contact]](mailto:[contact]).

End of Study Voicemail Script: Hi- this is [name] with my Digital Study. Whether you were able to quit or not, make sure to complete the outcome survey and Smokerlyzer assessment. Don't forget that everyone who finishes the study can earn up to \$150 in Amazon gift cards regardless of current quit status. Don't forget to fill out the (outcome survey + Smokerlyzer) before the link survey link expires on [date]!

### **15.13           End of Study: Thank you Letter SMS & Email**

Dear [Name],

On behalf of My Digital Study, we want to again thank you sincerely for your completed participation in the My Digital Study Smoking Cessation Study: Clinical Trial of an Innovative Digital Therapeutic for Smoking Cessation with Biochemical Verification.

We realize that participating in this study was time consuming and may have asked a lot of you. We value the time you committed to our research efforts. Your contributions will help others as a result of the medical and scientific knowledge gained from your participation. It is only with the help of volunteers like you that we can perform the essential research to find a new and effective treatment for smoking cessation.

If at any time you wish to access a public record of the study, you may locate this information on {clinicaltrials.gov/other registry domain} using the {NCT ID/registry identifier} {XXXX}.

Thank you very much again for your participation and for your contribution to medicine and to science!

Best Regards,

My Digital Study

#### **SMS:**

Congratulations! You have now completed the Smoking Cessation Study. Thank you very much again for your participation and for your contribution to medicine and to science! If you have any questions, please contact the research coordinator at [[contact]](mailto:[contact]) or [contact].

### **15.14           Participant Letter: EOS / Sponsor Reveal Letter**

Dear [Name],

Thank you for completing our smoking cessation study. Now that your participation in the study is complete, we wanted to disclose some additional information about the study. The sponsor of this study was Click Therapeutics, Inc., rather than "My Digital Study". The purpose of blinding the name of the study's sponsor was to avoid bias in your responses. Participants may have responded differently to surveys had they known that the developer of one of the apps being tested in the study, Clickotine, was sponsoring the study. We appreciate your honest answers and we hope that you continue on your quitting journey!

Thank you,

Click Therapeutics

### **15.15            Participant Letter: Lost to Follow up**

[Insert date]

Subject Line: Research Lost to Follow-up

Dear [Name],

This letter is being sent to you as a participant in the Digital Smoking Cessation Study. The Digital Study team has attempted to contact you in regard to a missing study activity/assessment that is required for the study. Our attempts to reach you by telephone, SMS, and email at [Insert telephone number(s)] on three separate occasions have been unsuccessful.

Participants who have not completed required activities or assessments after follow-up efforts per the protocol follow-up procedure will be considered as a lost to follow-up participant. Unfortunately, the My Digital Study team must discontinue your study participation, as reasonable efforts have been made by the research coordinator to retain your participation in the study and to complete study assessments within protocol specified timeline.

We realize that participating in this study was time consuming and may have asked a lot of you, but we value the time you committed to our research efforts.

Sincerely,

My Digital Study Team

### **15.16            How to use a Smokerlyzer Video Script**

Hi, I'm [name] from My Digital Study and today I'll be showing you how to use your new Smokerlyzer for the digital smoking cessation study. A Smokerlyzer is a handheld device used to measure the amount of carbon monoxide in your breath. We highly encourage you to use your Smokerlyzer throughout the study to track your progress and motivate you. Regular use of your Smokerlyzer will push you to see your carbon monoxide values drop and ensure that your Smokerlyzer is working properly. While not required, we would really appreciate it if you

submitted your values throughout the study. Doing so allows us to better support you throughout your journey and personalize your experience.

Your kit should come with an ICO Smokerlyzer, a white stereo cord, and a small visual diagram for further instructions.

Start by downloading the free Smokerlyzer app. This can be done by first opening the apple store or google play store on your mobile device. Go to the “search” tab of the store and tap the search bar. Type in “Smokerlyzer.” The Smokerlyzer app should be one the first results. Proceed to download the app.

[cut scene of [name] doing that]

When you open the app, the app will first ask for you preferred language. On the following the app will request a pin code. Your pin code will be on the back of your new Smokerlyzer. Input this pin code to proceed to the next page. Next, the app will ask for your Clinician’s name and email address. Enter “[name]” for the Clinician and “[[contact]](mailto:[contact])” for the email.

The next page will for your name and email address. Please enter your full name and your preferred email address.

[does that]

Now, you’re ready to use your Smokerlyzer. Plug the white cable cord into the Smokerlyzer and then into your phone’s headphone jack.

For those with an iPhone 7 or later, use an adapter to plug the smokerlyzer into your iPhone. One end of the adapter should plug into the other end of the white cable cord and the other end of the adapter should plug directly into the bottom of your iPhone. This adapter should have come with in the box when you purchased your iPhone.

[attaches wires]

With the app open and ready, select “new breath test.” Turn the volume on your mobile device to the maximum setting. On the top of your screen, you should see “device status: connected” in white font. Wait a few seconds for the program to load. Once loaded, the gray bar on the bottom will turn blue, stating “begin test.”

The program will first ask to take a deep inhalation and hold your breath for 15 seconds. After 15 seconds, the program will instruct you to exhale into the Smokerlyzer. Be sure to completely exhale all the air in your lungs. Readings will appear on your phone instantly.

[[name] holds breath]

After complete exhalation, wait a couple seconds for the program to load. Once loaded, the gray bar on the bottom will turn blue, stating “press to continue.” On the following page, the program will ask two questions about the number of cigarettes you smoke per day and how long you wait

until you smoke your first cigarette of the day. After filling out this information, press “continue.” The next page will provide a brief qualitative analysis of your smoking habits. On the following page, the program ask for a name and email address to share your results with. The name “[name]” and email address “[contact]” should already be appear in this section. If that content does not appear, enter that information manually. Next, select “send email.” A page will slide up displaying your email draft. Select “send” in the top right corner of the page. It is very important that you complete these instructions exactly so that information from your breath tests can be shared with my digital study.

[finish demonstration]

Congratulations, you’ve completed your first Smokerlyzer test.

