## **6.2 iCO Smokerlyzer**

Participants will receive an iCO Smokerlyzer to be used at the user's discretion periodically throughout the trial regardless of treatment group. At Week 4 (Day 28), participants will be asked to submit an exhaled CO assessment to ensure the Smokerlyzer works properly, to identify any issues and as an adherence check. At the time of the Outcome Survey, participants will be required to submit another exhaled CO assessment, which will be recorded as a study endpoint.

Upon completion of the Outcome Survey, participants will be invited to submit the CO assessment over a live video feed to confirm identity, until videos are received from 25 CKT users and 25 QG users. After 25 videos are received from each treatment group, participants will no longer be invited to submit the CO assessment over live video feed and will instead receive a reminder to remotely submit an exhaled CO assessment.

In order to conduct the CO assessment via live video monitoring, participants must have access to another device with video capabilities, such as another mobile device or computer. Participants that are invited to conduct the CO assessment via live video monitoring will consent to participate in live video monitoring at the end of the outcome survey by answering "Yes" or "No". Study participants that answer "Yes" and will then be linked to schedule a video call via Calendly with the research coordinator. Participants will have the option to select their preference of video platform on Calendly.

During the live video monitoring participants will be required to provide a personal ID to confirm identity. Participants who consent to participate in the live video CO assessment will receive an additional \$50 Amazon gift card for their participation.

Those who do not consent to participate in the live video monitoring CO assessment will receive a reminder to submit the end of study CO assessment.

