### **8.3 Assessment of Efficacy**

To assess 30-Day Sustained Abstinence from Smoking (NACQ, 2016) participants are asked the following questions in the Outcome Survey to determine Russell Standard Self- Reported 4-Week Quitter status (West et al., 2005):

1. Have you smoked (even a puff) in the last 30 days?

- a. Yes
- b. No

2. (If yes, this question will appear) Have you smoked (even a puff) in the last 14 days?
  - a. Yes
  - b. No
3. (If yes, this question will appear) Have you smoked (even a puff) in the last 7 days?
  - a. Yes
  - b. No

The Outcome Survey will instruct subjects to submit an exhaled carbon monoxide (CO) reading with the iCO Smokerlyzer they were mailed after participant randomization. iCO Smokerlyzer devices will be programmed to email the exhaled carbon monoxide measurement results to the research coordinator directly.

The primary outcome, 30-day abstinence from smoking, will be assessed via self-report on the outcome survey. Confirmation with the remote CO assessment will be conducted to assess concordance between self-report and remote CO assessment results. Abstinence as per the CO assessment will be defined as an iCO reading of fewer than 7ppm exhaled CO.

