#### **10.4 Secondary Endpoint**

Concordance rates between self-reported 30-day abstinence and the remote CO monitoring result will be estimated, with concordance > 85% considered evidence of a valid reporting process by Magellan Behavioral Health. Concordance rates will be compared between users that submit the CO measurement under video monitoring and those that do not. Upon completion of the Outcome Survey, participants will be invited to submit the CO assessment over a live video feed to confirm identity, until videos are received from 25 CKT users and 25 QG users. After 25 videos are received from each group, participants will no longer be invited to submit the CO assessment over live video feed.

Secondary analysis of the subgroup of NRT/pharmacotherapy users will be conducted to compare cessation rates between the CKT+NRT group and the CKT-only group, to confirm the initial trial result that CKT+NRT is not superior to CKT-alone.

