#### **10.5 Sample Size**

Power analysis: Estimated ITT 30-day cessation rates after 8-weeks of use for CKT and QG are based on published reports: CKT 26.2%, QG 8.3%. A power analysis for logistic regression using g\*Power 3.1 software was conducted with the following parameters: 85% power to detect a group difference with  $\alpha = 0.05$  two-sided significance level, and estimated Group 1 proportion,  $p_1$ , of 0.262 and a Group 2 proportion,  $p_2$ , of 0.083. A sample size of 78 subjects in each group will yield 85% power to detect such a difference. To obtain this sample size, we plan to obtain consent from 195 subjects and enroll 156 into the study by downloading the assigned app, which reflects a conservative approach to the retention rate observed in our pilot data.

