**Smokerlyzer instructions for use:**

1. Plug the white cord into the Smokerlyzer and into your phone's headphone jack
2. Take a deep breath and hold it for 15 seconds
3. Exhale into the Smokerlyzer
4. Readings will appear on your phone instantly
5. Results will be explained and charted

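### The timing of the week-8 CO test is neither set nor recorded, so a smoker with a low waking reading could be counted as abstinent in the concordance endpoint

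*Protocol*

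**What the plan says.** Protocol 3.1 has everyone take the end-of-study CO test whatever smoking status they report. Section 7.10 allows Days 53 to 59. Within that window the visible materials fix only the technique:

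- The video script (15.16) says "The program will first ask to take a deep inhalation and hold your breath for 15 seconds".
- The instruction cards (15.5 and the printed card at the end of Appendix 15) say "Take a deep breath and hold it for 15 seconds".
- The prompt sent after the outcome survey (15.11) says "Please remember to submit your Smokerlyzer CO assessment if you have not done so already".
- The Day 53 and Day 56 messages and the voicemail scripts (15.10 to 15.12) ask for the test without naming an hour.

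Section 8.3 gives the rule: "Abstinence as per the CO assessment will be defined as an iCO reading of fewer than 7ppm exhaled CO". Section 11.1 lists the ppm value as the CO data item, with no test time. The SAP does the same under Data Acquisition, but with a cut-off of below 8 ppm.

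Participants who agree to video monitoring "will then be linked to schedule a video call via Calendly with the research coordinator" (6.2). The others test when they choose. Section 10.4 treats concordance above 85% as evidence of a valid reporting process and adds a comparison: "Concordance rates will be compared between users that submit the CO measurement under video monitoring and those that do not".

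**The concern.** A single CO reading reflects recent smoking, so its meaning depends on how long ago the person last smoked. The trial enrols people who smoke as few as 5 cigarettes a day (4.2). If CO clears appreciably overnight, some current smokers who test on waking could fall under the cut-off, and the plan's rule would call them abstinent.

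Two errors follow. A truthful smoker becomes a disagreement between report and reading. A person who falsely claims to have quit is confirmed. Because no test time is recorded, the analysis could not tell either error from a real reporting problem.

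What is at stake is the secondary objective in 2.2 and the wish, stated in the SAP's protocol summary, to base reimbursement on remote CO verification. Section 2.2 also reads the absence of a difference between video and non-video participants as support for both procedures. That reading is weaker if the two groups test at different hours.

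**Working it through.** **The plan's own figure.** Section 10.5 plans 78 per arm for 26.2% against 8.3%, two-sided 0.05, 85% power. The pooled two-proportion formula gives 79 per arm, and 84.8% power at 78, so the figure reproduces. The present point does not depend on it. The plan gives no figure for CO timing or concordance beyond the 85% benchmark.

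**Step 1: could a smoker read below 7 ppm on waking?** The documents give no clearance rate. Assume single-exponential decline with half-life h, 8 hours without smoking and no background CO. The highest bedtime level that falls to the cut-off is cut-off × 2^(8/h).

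| Half-life (h) | Limit at 7 ppm | Limit at 8 ppm (SAP) |
|---|---|---|
| 4 | 28.0 | 32.0 |
| 5 | 21.2 | 24.3 |
| 6 | 17.6 | 20.2 |
| 8 | 14.0 | 16.0 |

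One hour after a cigarette the limit at 7 ppm is only 7 × 2^(1/h), or 8.3 to 7.6 ppm for h from 4 to 8. Under this assumption the time since smoking matters a great deal. The table does not show how many participants have bedtime levels under these limits.

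**Step 2: effect on two-way concordance.** Inputs: 156 randomized and the two planning rates (10.5); pilot completion 365 of 416, or 87.7% (1.3).

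- Responders: 156 × 365/416 = 136.9.
- Claimed abstainers: 78 × (0.262 + 0.083) = 26.9, so q = 26.9/136.9 = 0.197.
- Reported smokers: 136.9 − 26.9 = 110.0.

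Assume that every report is true, every responder sends a reading, and all true abstainers read below the cut-off. If a share f of honest smokers reads low, concordance = 1 − (1 − q) × f.

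| f | Concordance |
|---|---|
| 5% | 96.0% |
| 10% | 92.0% |
| 15% | 88.0% |
| 20% | 83.9% |
| 30% | 75.9% |

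Break-even: f = 0.15/(1 − q) = 0.15/0.803 = 18.7%, about 21 of 110 smokers. For q = 0.08 it is 0.15/0.92 = 16.3%; for q = 0.30 it is 0.15/0.70 = 21.4%.

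**Step 3: if concordance covers claimed abstainers only.** Let g be the share of claims that are false and f the share of those people who read low. Concordance is 1 − g × (1 − f), which rises with f. Low readings then inflate the rate.

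**Step 4: video comparison.** There would be 50 video readings and about 137 − 50 = 87 others. With f at 5% in one group and 20% in the other, concordance is 96.0% against 83.9%, a gap of about 12 points from timing alone. With equal f the gap is zero. These shares are illustrations.

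**The case against.** The strongest reply is that the causal step and its frequency both come from outside the documents. No passage gives a CO half-life, a typical smoker's reading or the distribution of test hours. The 19% is a break-even value found by working back from the benchmark, and at 15% the benchmark is still met. The test is prompted when the outcome survey is completed, and nothing suggests that tests cluster at waking. Payment does not depend on quit status, so participants have no financial reason to time a test to pass. All of this stands, and it limits the point to a possible error of unknown size.

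Three stronger readings are tempting, and the documents do not support them.

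- A reader might infer that the video comparison is confounded by hour. The plan says only that one group books an appointment and the other does not. It states no hours, and equal timing gives no bias. The comparison is in any case exposed to self-selection through consent, the need for a second device and the extra $50.
- A reader might infer that the primary result is compromised. Protocol 8.3 and 10.3 and SAP 10.3 define the primary endpoint by self-report alone. CO enters it only under the wording of 3.1, which combines self-report with a reading below 7 ppm.
- A reader might infer that participants receive no timing advice at all. The diagram packed with the device, the app's own screens and the consent pages cannot be seen here, so the claim is limited to the visible text.

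Timing is also not the only source of disagreement. Someone who smoked within 30 days but not recently is discordant at any hour. Finally, restricting the main analysis to readings taken in set hours would discard data, including from a video group capped at 25 per arm; the fix avoids that.

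**Conclusion.** The omission is confirmed in the visible text: no hour, time since waking or time since last cigarette is set for the week-8 CO test, and no test time is listed as data. Given the assumed clearance (half-life 4 to 8 hours, 8 hours overnight), a waking reading under 7 ppm is possible for bedtime levels up to about 28 to 14 ppm. The documents do not show how often this would occur.

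Under two-way concordance with true reports, the benchmark fails once roughly 19% of honest smokers read low, with a range of 16% to 21%. Under concordance among claimed abstainers, the same error pushes the rate up. Section 10.4 does not say which definition applies, so the net direction is open. The effect on the video comparison is possible but not shown. The point concerns the secondary concordance endpoint and is worth acting on because the remedy is cheap and the missing test times may be hard to recover later.

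**What to change.** - **Instruction.** Add one sentence to 6.2, 8.2, both cards, the video script, and the Day 53, Day 56 and CO-prompt messages: take the end-of-study test later in the day (afternoon or evening) and not on waking.
- **Video calls.** Offer appointment slots in the same hours.
- **Data.** Record the date and time of each reading from the e-mail that already delivers it, and add one item for time since last cigarette or since waking.
- **Analysis (10.4 in both documents).** Keep all readings in the main concordance analysis. Report concordance separately for self-reported quitters and self-reported smokers. Add a sensitivity analysis limited to readings taken in the requested hours, for the overall rate and the video comparison.
- **Reconcile** the cut-off: below 7 ppm in Protocol 8.3 and 11.1, below 8 ppm in the SAP's Data Acquisition text.

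The cost is revised message wording, a calendar setting, one or two data fields and a few sentences in the analysis plan. Participants bear slight inconvenience. Sample size and treatment do not change. The exact hours are for the sponsor to choose, since the documents give no basis for a particular limit.
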